### **7.1.3.2 Pregnancy Test**

All women who are being considered for participation in the trial, and who are not surgically sterilized or postmenopausal, must be tested for pregnancy within 72 hours of each cycle of trial treatment and 30 days post-treatment. If a urine test is positive or not evaluable, a serum test will be required. Subjects must be excluded/discontinued from the trial in the event of a positive or borderline-positive test result.

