### **4.1.3 Pre-clinical and Clinical Trials**

#### **4.1.3.1 Preladenant**

Safety pharmacology and toxicology studies have demonstrated a generally favorable safety profile for preladenant (see the IB for further details).

In dogs, hepatic changes and increases in heart rate (28% to 45% in first 8 hours after dosing) and blood pressure (BP; 10% to 12% in the first 8 hours after dosing) support the continued and careful monitoring of these parameters during clinical investigations.

Results of a definitive embryo-fetal development study in rabbits indicate a non-dose-related low incidence of increases in cardiac malformations at all doses of preladenant. However, in a second rabbit embryo-fetal developmental toxicity study at the same doses, the results of the first study were not confirmed. Consequently, the reasons for the cardiac findings in the first study are unknown but may be due to genetic variability. Nevertheless, potential embryo/fetal exposure in women should be avoided.

In addition, genetic toxicology studies and carcinogenicity studies indicate no evidence of mutagenic or carcinogenic potential. In animals and humans, preladenant metabolism includes O-demethylation to an alcohol (SCH 434748) and subsequent oxidation to a carboxylic acid (SCH 446637), as well as N-dealkylation and alterations to the furan ring. Both SCH 434748 and SCH 446637 are also selective, high-affinity A2a receptor antagonists.

A total of 38 clinical trials were conducted with preladenant (see the IB for further details). In Phase 1, 24 clinical studies in healthy volunteers have been completed. In Phase 2, 8 clinical studies have been completed in subjects with drug-induced movement disorders and subjects with idiopathic Parkinson's disease. Four Phase 3 trials in subjects with Parkinson's disease have been also completed.

Approximately 3300 subjects have received preladenant in the Parkinson's disease clinical program. Doses have ranged from 2 to 200 mg/day and have been administered as a single dose or BID for up to 1 year. In general, preladenant was generally well tolerated in these trials (see IB for preladenant).

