## **5.8 Subject Withdrawal/Discontinuation Criteria**

### **5.8.1 Discontinuation of Treatment**

Discontinuation of treatment does not represent withdrawal from the trial.

As certain data on clinical events beyond treatment discontinuation may be important to the study, they must be collected through the subject's last scheduled follow-up, even if the subject has discontinued treatment. Therefore, all subjects who discontinue trial treatment prior to completion of the treatment period will still continue to participate in the trial as specified in Section 6.0 - Trial Flow Chart and Section 7.1.5. – Visit Requirements .

Subjects may discontinue treatment at any time for any reason or be dropped from treatment at the discretion of the investigator should any untoward effect occur. In addition, a subject may be discontinued from treatment by the investigator or the Sponsor if treatment is inappropriate, the trial plan is violated, or for administrative and/or other safety reasons. Specific details regarding procedures to be performed at treatment discontinuation are provided in Section 7.1.4 – Other Procedures.

A subject must be discontinued from treatment but continue to be monitored in the trial for any of the following reasons:

- The subject or subject's legally acceptable representative requests to discontinue treatment.
- Non-compliance with trial treatment or procedure requirements.
- A confirmed positive serum pregnancy test.
- Confirmed radiographic disease progression outlined in Section 7.1.5 (exception if the Sponsor approves treatment continuation).
  - A subject with confirmed radiologic progression may continue to receive study treatment, after consultation with the Sponsor, if the investigator deems the subject is receiving clinical benefit or value from treatment.
- Unacceptable adverse experiences as described in Section 7.2.
- Intercurrent illness other than another malignancy as noted above that prevents further administration of treatment.
- Investigator's decision to discontinue treatment.
- Recurrent Grade 2 pneumonitis.
- Progression or recurrence of any malignancy, or any occurrence of another malignancy that requires active treatment.
- Completion of 35 treatments with preladenant and/or pembrolizumab.

Note: 35 cycles (approximately 2 years) are calculated from the first dose

- Administrative reasons.

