Blood for Stimulation Assay 		X			X							
PBMC for Biomarker Analysis 	X			X 		X 						
Serum for Cytokine Analysis 		X			X		X					
Plasma Collection for Proteomic Analysis 		X	X	X	X		X					
Urinalysis 	X											
Chemistry 	X	X	X	X	X	X	X		X	X		

Preladenant in Monotherapy (Arm 1 ; Part 1)												
	Screening	Treatment Phase						Tumor Assessment	End of Treatment	Post-treatment Follow-Up Phase		
		Cycle 1			Cycle 2-4		Cycles 5 and all Subsequent Cycles	Every 9 weeks	Discontinuation	Safety Follow-up		Survival Follow-Up 
		Day 1	Day 8	Day 15	Day 1	Day 15	Day 1		At Treatment Discontinuation	30 days after the last dose	90 days after the last dose	Every 12 weeks post discontinuation
Scheduling Window (Days) 	-28 to -1	+3	±3	±3	±3	±3	±3	±7		+7	+7	±7
Prothrombin Time (PT)/International Normalized Ratio (INR) and Activated Partial Thromboplastin Time (aPTT) 	X											
Serum or Urine Pregnancy Test – if applicable 	X	X										
On-treatment Tumor Biopsy 					X							
Pharmacokinetics Evaluations												
Blood for preladenant PK assay 		X	X	X	X		X					

AE = adverse event; ALT = alanine aminotransferase; AST = aspartate aminotransferase; BUN = blood urea nitrogen; CR = complete response; CT = computed tomography; ECG = electrocardiogram; ECOG = Eastern Cooperative Oncology Group; min = minute; PGt = pharmacogenetic; PK = pharmacokinetic; PR = interval between the P wave and the QRS wave; QRS = interval from onset of the Q wave to end of the S wave; QT = interval from onset of the QRS complex to end of the T-wave; QTcF = QT interval corrected for heart rate; SAE = serious adverse event; SGOT = serum glutamic oxaloacetic transaminase; SGPT = serum glutamic pyruvic transaminase.

1. Visits should occur within the prespecified days window (e.g. +/- 3d).
2. Screening procedures to be performed within 28 days prior Cycle 1 Day1 (C1D1), unless otherwise noted. Informed consent may be obtained more than 28 days prior to C1D1 to allow for tumor tissue collection pre-treatment.
3. Subject Identification Card must be given to Subject at the start of study and must be collected when the Subject is no longer participating in any portion of the study.

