20. Urine dipstick or microscopic urinalysis may be performed according to site SOP. Urine dipstick includes pH, protein, glucose, leukocyte-esterase, ketones, and nitrite. Mandatory microscopic urinalysis will be performed if the dipstick results are abnormal. Microscopic analysis includes white blood cell count, red blood cell count, epithelial cells and casts.
21. Serum Chemistry tests include sodium, potassium, calcium, phosphate, chloride, bicarbonate/CO2 (if performed in region), BUN or Urea, creatinine (Cystatin C if abnormal), SGOT (AST), SGPT (ALT), total proteins, total bilirubin (direct bilirubin if abnormal), albumin, alkaline phosphatase, glucose, uric acid, amylase, lipase, Lactate Dehydrogenase (LDH) and  $\gamma$ -glutamyltransferase (GGT). Serum chemistry does not need to be repeated on C1D1 if screening samples were obtained within 3 days of C1D1.
22. Coagulation factors (PT/INR and aPTT) should be tested as part of the screening procedures for all subjects. Furthermore, any subject receiving anticoagulant therapy should have coagulation factors monitored closely throughout the trial.
23. For women of reproductive potential, a urine pregnancy test will be performed at Screening and within 72 hours prior to the first dose of study treatment. If a urine pregnancy test cannot be confirmed as negative, a serum pregnancy test is required and should be negative. Additional pregnancy testing should be conducted as per local regulations where applicable.
24. On-treatment tumor biopsy will be performed on Day 15 of Cycle 2 (+/- 7 Days). Tumor tissue will be sent to designated laboratory for biomarker analysis and leftover tissue may be saved for future biomedical research if the subject signs the FBR consent.
25. Procedures for collection of PK samples and precise time points are described in the Procedures Manual. Samples for preladenant and its metabolites pharmacokinetic (PK) testing should be collected prior to dosing, and 1 hour, 2 hours, 4 hours and 8 hours after drug administration of preladenant (+/- 10 minutes) on Cycle 1 Day 1 and Cycle 2 Day 1; Prior to dosing on Cycle 1 Day 8; Prior to dosing on Cycle 1 Day 15; Prior to dosing on Cycle 4 Day 1; And, Prior to dosing on Cycle 8 Day 1. If the sample day falls on a weekend or a holiday, please consult the Sponsor for alternate sample collection times.

Preladenant in Combination with Pembrolizumab (Arm 2 ; Part 1 and Part 2) and (cross-over subjects)												

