21. Urine dipstick or microscopic urinalysis may be performed according to site SOP. Urine dipstick includes pH, protein, glucose, leukocyte-esterase, ketones, and nitrite. Mandatory microscopic urinalysis will be performed if the dipstick results are abnormal. Microscopic analysis includes white blood cell count, red blood cell count, epithelial cells and casts.
22. Serum Chemistry tests include sodium, potassium, calcium, phosphate, chloride, bicarbonate/CO2 (if performed in region), BUN or Urea, creatinine (Cystatin C if abnormal), SGOT (AST), SGPT (ALT), total proteins, total bilirubin (direct bilirubin if abnormal), albumin, alkaline phosphatase, glucose, uric acid, amylase, lipase, Lactate Dehydrogenase (LDH) and  $\gamma$ -glutamyltransferase (GGT). Serum chemistry does not need to be repeated on C1D1 if screening samples were obtained within 3 days of C1D1.
23. Coagulation factors (PT/INR and aPTT) should be tested as part of the screening procedures for all subjects. Furthermore, any subject receiving anticoagulant therapy should have coagulation factors monitored closely throughout the trial.
24. For women of reproductive potential, a urine pregnancy test will be performed at Screening and within 72 hours prior to the first dose of study treatment. If a urine pregnancy test cannot be confirmed as negative, a serum pregnancy test is required and should be negative. Additional pregnancy testing should be conducted as per local regulations where applicable.
25. Samples for thyroid function testing should be collected at screening, on Day 1 of Cycle 1 and on Day 1 of Cycle 2. Following Cycle 2, testing will be performed on Day 1 of every other cycle (i.e. Cycles 1, 2, 4, 6, etc.), at discontinuation, and at the 30 days Safety Follow-up Visit. Analysis of T3 or FT3, FT4 and TSH will be performed by the local study site laboratory (or by central vendor if testing is not available at the local study site laboratory).
26. ADA samples for pembrolizumab will be collected within 24 hours before infusion in cycles 1, 2, 4, 8 and every 4 cycles thereafter, 30 days after discontinuation of study drug (or until the subject starts new anti-cancer therapy). Please refer to the procedure manual for detailed sampling timepoints.

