### 7.1.3 Laboratory Procedures/Assessments

Details regarding specific laboratory procedures/assessments to be performed in this trial are provided below. The total amount of blood/tissue to be drawn/collected over the course of the trial (from pre-trial to post-trial visits), including approximate blood/tissue volumes drawn/collected by visit and by sample type per subject can be found in the Study Procedures Manual. Refer to the Trial Flow Chart (Section 6.0) for the schedule of laboratory assessments.

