**7.1.3.1 Laboratory Safety Evaluations (Hematology, Chemistry and Urinalysis)**

Laboratory tests for hematology, chemistry and urinalysis are specified in [Table 13](#).

Table 13 Laboratory Tests

Hematology	Chemistry	Urinalysis	Other
Hematocrit	Albumin	Blood	Pregnancy test (serum or urine) a
Hemoglobin	Alkaline phosphatase	Glucose	PT/INR
Platelet count	Alanine aminotransferase	Protein	aPTT
WBC (total and differential) e	Aspartate aminotransferase	Specific gravity	Total T3 or free T3, FT4, and TSH b,d
RBC	Bicarbonate/CO 2 c	Microscopic exam, if abnormal results are noted	
Absolute lymphocyte count	Calcium		
Absolute neutrophil count	Chloride		
	Creatinine (Cystatin C if abnormal)		
	Glucose		
	Phosphorus		
	Potassium		
	Sodium		
	Total bilirubin		
	Direct bilirubin		
	Total protein		
	GGT		
	Blood urea nitrogen		
	Uric acid		
	Amylase		
	Lipase		
	LDH		

a Perform on women of childbearing potential only 72 hours prior to Day 1 of Cycle 1. Pregnancy tests must be repeated prior to every cycle if required or as specified per local regulatory guidance.
 
b T3 is preferred; if not available free T3 may be tested.
 
c If this test is not done as part of local standard of care, this test does not need to be performed.
 
d If the local laboratory is unable to perform these tests, the site should submit the sample to the central laboratory for testing. Details are provided in the Procedure Manual.
 
e Report % or absolute results per standard of practice. Report the results in the same manner throughout the trial.
 
aPTT=activated partial thrombin time; FT4=free thyroxine; GGT=gamma-glutamyl transferase; INR=insulin receptor; PT=prothrombin time; RBC=red blood cells; T3=triiodothyronine; TSH=thyroid stimulating hormone (thyrotropin); WBC=white blood cells.
			

Laboratory tests for screening should be performed within 3 days prior to the first dose of trial treatment. An exception is hepatitis and thyroid serologies, which may be performed within 28 days prior to first dose. After Cycle 1, pre-dose laboratory safety tests can be conducted up to 72 hours prior to dosing unless otherwise noted on the flow charts.

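### Section 7.1.3.2 requires a pregnancy test at every cycle and 30 days post-treatment, but the flow charts and Table 13 schedule none after the first dose unless local rules ask for it

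*Combined protocol and SAP*

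**What the plan says.** Four places in the current protocol text set the pregnancy-testing schedule.

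- **Section 7.1.3.2** covers women who are not surgically sterilized or postmenopausal. They "must be tested for pregnancy within 72 hours of each cycle of trial treatment and 30 days post-treatment". The requirement is unconditional.
- **Section 6.1, both flow charts** (Arm 1; and Arm 2 with Part 2 and cross-over subjects). The row "Serum or Urine Pregnancy Test" is marked at Screening and Cycle 1 Day 1. Every later column is empty, including the later cycles, discontinuation and the 30-day and 90-day safety follow-up.
- **Flow-chart footnotes 23 (Arm 1) and 24 (Arm 2).** Both apply to women who could become pregnant and say: "a urine pregnancy test will be performed at Screening and within 72 hours prior to the first dose of study treatment". After that, "Additional pregnancy testing should be conducted as per local regulations where applicable".
- **Section 7.1.3.1, Table 13, footnote a.** A test is required before Cycle 1 Day 1. Then "Pregnancy tests must be repeated prior to every cycle if required or as specified per local regulatory guidance". No post-treatment test appears.

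On which text a site should use, Section 7.1 describes the flow chart as a summary of procedures that are detailed in the sections after it. Section 7.1.3, which introduces the laboratory procedures, says: "Refer to the Trial Flow Chart (Section 6.0) for the schedule of laboratory assessments".

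**The concern.** The same protocol gives two different rules for one safety test. A site that builds its visit checklists from the flow chart, as Section 7.1.3 directs, would plan no pregnancy test after the first dose in any country whose rules are silent. It would then depart from Section 7.1.3.2 at every later cycle and again at 30 days.

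The protocol treats pregnancy on treatment as serious. Section 4.1.3.1 concludes that "potential embryo/fetal exposure in women should be avoided". Section 5.7.2 says either drug may harm a fetus. Section 5.8.1 lists "A confirmed positive serum pregnancy test" among the reasons treatment must stop, and Section 5.7.3 makes that stop immediate. A stopping rule that depends on a test works only if the test is done. Treatment can run to 35 cycles, so the untested period can be long. In a worldwide trial, practice would also differ by country.

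**Working it through.** No sample-size, power or error-rate figure is involved, and the plan gives no figure of its own to reproduce. The check sets the texts side by side and counts tests.

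**Comparison by time point**

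| Time point | Section 7.1.3.2 | Flow charts, footnotes 23 and 24 | Table 13, footnote a |
|---|---|---|---|
| Screening | not named | required | not named |
| Before Cycle 1 | required | required | required |
| Before each later cycle | required | local rules only | if required, or per local guidance |
| 30 days post-treatment | required | no mark; local rules only | not mentioned |

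The texts agree only on the test before Cycle 1.

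**Are the empty columns a table-reading artefact?** No. The footnotes state in prose what the marks show. In the same charts, hematology and chemistry are marked at the later cycles and at the 30-day visit.

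**Is it left over from an amendment?** No. The summary of changes does not mention pregnancy testing, and all the texts compared are current.

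**Count of tests after the first dose**, for a woman treated for n cycles, leaving Screening aside:

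- Section 7.1.3.2: n cycle tests + 1 at 30 days = n + 1. One of these comes before the first dose, so (n + 1) − 1 = n come after it.
- Flow charts, where local rules add nothing: 1 before the first dose and 0 after it.

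| Cycles received, n | Section 7.1.3.2, after first dose | Flow charts, after first dose |
|---|---|---|
| 3 (63 days, the first 9-week scan) | 2 + 1 = 3 | 0 |
| 6 | 5 + 1 = 6 | 0 |
| 35 (maximum) | 34 + 1 = 35 | 0 |

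The count is for one course on one chart. If the Arm 2 chart is applied from its start when a woman crosses over from Arm 1, it would add its own Screening and Cycle 1 Day 1 tests, and again none after those.

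**The case against.** Four points can be made for the plan.

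1. **The detailed text governs.** Section 7.1 calls the chart a summary, Section 7.1.3.2 is the detailed and mandatory text, and the footnotes do not say that later tests are unnecessary. A site reading the whole protocol would test every cycle. This lowers the chance of error but does not remove it. Section 7.1.3 points back to the chart for the laboratory schedule, and Section 7.1.4.3 does so for the Day 1 procedures before dosing. The footnotes are also not silent: they state a different rule, conditional on local regulations.

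2. **Table 13 may not conflict.** The words about repeats being required stand apart from local guidance and could refer back to Section 7.1.3.2. That reading is possible but less natural. It leaves the flow-chart footnotes unchanged and supplies no 30-day test.

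3. **Other safeguards exist.** A negative test is needed before the first dose, and contraception is required through 120 days after the last dose. Subjects expecting to conceive are excluded, and those unlikely to use contraception reliably should not be entered. Pregnancies must be reported within 24 hours. The rabbit finding behind the Section 4.1.3.1 statement was not confirmed in a second study. These points reduce the risk and stand as mitigation. None of them detects a pregnancy during treatment, and the reporting duty in Section 7.2.2 covers pregnancies that are spontaneously reported.

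4. **The texts could be aligned the other way**, by weakening Section 7.1.3.2. Inclusion criterion 9 and Section 7.1.5.1 name only pre-treatment tests, so the sponsor could argue for this. It would resolve the contradiction, but it would drop a protection now stated as mandatory and would sit poorly with Sections 4.1.3.1, 5.7.2, 5.7.3 and 5.8.1.

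**Conclusion.** The concern holds. The current text contradicts itself on a mandatory safety test, in both arms, in Part 2 and for cross-over subjects. Where local rules add nothing, the shortfall is n tests for a woman treated for n cycles, up to 35.

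These are counts of tests, not of undetected pregnancies. The documents give neither the number of women of childbearing potential nor the number of sites whose local rules require repeat testing, so the practical size cannot be estimated. The upper figure assumes all 35 cycles are given; many subjects with pretreated advanced tumors may stop sooner. No endpoint, estimate or analysis changes. The point should be corrected for subject safety and consistent conduct.

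**What to change.** Let Section 7.1.3.2 govern and bring the other texts into line.

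- In both Section 6.1 flow charts, add pregnancy-test marks at Day 1 of Cycles 2-4, at Day 1 of Cycle 5 and all later cycles, and at the 30-day Safety Follow-up visit.
- Amend footnote 23 (Arm 1), footnote 24 (Arm 2) and Table 13 footnote a to read, in substance: women of childbearing potential are tested in the 72 hours before each cycle and at 30 days post-treatment; local regulations may add tests but not remove them.

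The cost is the wording, the chart marks, and one urine test per later cycle plus one at 30 days for the women concerned. Section 7.1.3.2 already requires these tests, so no procedure is new. No extra visit is needed: Day 1 and the 30-day visit already include hematology and chemistry, and Section 7.1.3.1 already allows laboratory safety tests up to 72 hours before dosing after Cycle 1.

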### **7.1.3.3 Pharmacokinetic/Pharmacodynamic Evaluations**

#### **7.1.3.3.1 Blood Collection for PK Assessment for Preladenant**

Samples for PK evaluations for preladenant will be collected at the timepoints outlined in Section 6.0 – Trial Flow Chart. Sample collection, storage and shipment instructions for blood samples will be provided in the Procedures Manual.

#### **7.1.3.3.2 Blood Collection for PK and ADA Assessment for Pembrolizumab**

To further evaluate pembrolizumab immunogenicity and exposure of the proposed dosing regimen, sample collections for analysis of antidrug antibodies (ADA) and PK are currently planned as shown in the Trial Flow Chart (Section 6.0). Blood samples will be obtained to measure PK of serum pembrolizumab. The pembrolizumab serum maximum concentration (Cmax) and minimum concentration (Ctrough) at planned visits and times will be summarized.

If ongoing ADA and/or PK results continue to be consistent with existing ADA and/or PK data from other pembrolizumab clinical trials, it may be decided to discontinue or reduce further sample collection in this trial. Should this occur, it will be communicated by an administrative memo.

Pharmacokinetic data will also be analyzed using nonlinear mixed effects modeling. Based on PK data obtained in this trial as well as PK data obtained from other studies, a population PK analysis will be performed to characterize PK parameters (clearance [CL], volume of distribution [V]) and evaluate the effect of extrinsic and intrinsic factors to support proposed dosing regimen. Pharmacokinetic data will also be used to explore the exposure response relationships for pembrolizumab antitumor activity/efficacy as well as safety in the proposed patient population, if feasible. The results of these analyses, if performed, will be reported separately.

